## 6.4 Lost to Follow-Up

Participant status of lost to follow-up will be minimized and retention maximized through various mechanisms to collect study survey responses. The following options will be available: in person, via phone, or a web-based link, text or email. Study staff should confirm the best contact information for the participant at each study encounter.

Additionally, data collected from the EHR and Medicare and Medicaid claims data (see Section 9 for details) will be robust to missing data due to participants that are lost to follow up.

## 6.5 Risk

The potential risks described below are minimal and reasonable in relation to the potential benefit for genotype-guided therapy to improve the management of pain and depression and reduce the pain and depression burden to society.

### Blood Draw

The risks of a blood draw include pain, bruising, and the slight possibility of infection at the place of needle insertion. Some people feel dizzy or may faint during or after a blood draw.

### Off FDA label use of antidepressants

In the depression trial, specifically in the pediatric population, the standard practice of medicine may include use of antidepressants that are currently not FDA approved to treat depression in pediatrics. Use of drugs not labeled for use in pediatrics, but prescribed by their treating physician, is not a risk due to study participation.

### Prescription Changes

It is possible that the PGx-PGx-recommended drug therapy change may lead to worse pain control or worse control of depression symptoms, though the likelihood is that is no different than with the usual trial and error approach typically used for defining pain management or antidepressant therapy. Pharmacogenetic information is expected to lead to safer and more effective drug therapy, and the ultimate prescribing decision in this study will be left to the physicians. Thus, there are no anticipated risks with basing therapy on pharmacogenetic test results and our preliminary data support a clinical benefit, not risk.

### Genetic Information Privacy

The risks of study participation are primarily those related to genetic studies, including risks related to confidentiality surrounding the genetic information and the chance that the genetic information could in some way expose the participant to increased risk regarding employment or that future life, health, disability or long-term care insurance providers could potentially use this genetic information to deny, limit or raise rates for insurance coverage. The Genetic Information Nondiscrimination Act (GINA) makes it illegal for health insurance companies, group health plans, and most employers to discriminate based on genetic information, but other insurers may still use genetic information to discriminate. The pharmacogenetics examples included in our study are only known to be associated with drug response, which is unlikely to lead to insurance discrimination as long as effective, alternative therapies are available, as they are for all gene-drug pairs included in this study.

## 6.6 Benefit

Study participation may not directly benefit participants of the study especially those who do not have an actionable phenotype. It is possible however that those individuals who have an actionable phenotype may benefit from this study.

### Improved drug therapy

The genotype information could lead to improved drug therapy management for select participants. For example, CYP2D6 genotype may help to identify participants unlikely to respond to codeine, tramadol, or hydrocodone or who are at high risk for toxicity with these opiates plus oxycodone. This could lead to prescribing of alternative opiates or other non-opioid therapies more likely to reduce pain without compromising participant safety. In addition, through improved pain management and use of lower potency opioids in individuals expected to respond well to these drugs based on genotype, the study may indirectly have positive impacts on the opioid crisis by helping to reduce the individual participant opioid burden.

Similar to the above, potential benefits exist for the SSRIs based on more appropriate dosing or selection of an alternative antidepressant. Finally, participants may benefit from optimized therapy for other drugs that may have recommendations based on the panel-based pharmacogenetic testing.

Though the study participants that are randomized to the usual care/control arm have no potential to derive benefit during their participation in the clinical trial, when they complete the 6-month follow-up, they will have their genotype recorded in the EHR, whereby it could be used to guide any future relevant therapies.

## **6.7 Costs to the Participants**

The cost of clinical genotyping and collection of PRO outcomes will be covered by the clinical trial. The cost of their drug therapy will not be covered by the trial since they would be prescribed a medication regardless of participation in the trial. However, taking part in this study may lead to added costs to the participant, specifically the costs of their care, including the physician-prescribed drug therapy, which will generally be covered by the participant's insurance (if insured), and will not be covered by the study.

## **6.8 Compensation to Participants**

Participants will be reimbursed for their time and effort, prorated by study completion. Sites will follow local policies and procedures for amount, timing of, and mechanism for issuing compensation to participants. Participants may be reimbursed for travel or parking expenses per institutional specific policies.

## 7. STUDY PROCEDURES

An overview of the study procedures to be followed is presented in this section. Recruiting sites will receive training on the protocol and MOP before site activation for enrollment.

### 7.1 Interventions/Treatments

The intervention, genotype-guided pain or depression therapy, is intended to reflect the practices and procedures that are likely to be implemented if PGx testing were to be integrated into standard clinical practice. The intervention has two technical components: the PGx panel testing and the clinical decisions support/clinical recommendations for providers, described below. The participant and provider facing components of the intervention include the following:

#### Patient Participants

- The return of the PGx testing results to the participant's medical record that is analogous to typical lab results. Participants may discuss their results with their provider.

#### Providers

- The return of PGx testing results to the participant's provider via standard site-specific laboratory return of results methods
- Clinical decision support will be provided to all providers, how that is provided may vary. At least one of the two options below that includes drug-drug interactions, is required.
  - a. A static report/consult note with interpretation of the genetic testing results and drug-drug interactions, and treatment recommendations
  - b. Where possible, a provider prescribing alert for actionable phenotypes, triggered when a relevant opioid or SSRI medication is ordered that indicates the participant's genetic results and/or metabolizer phenotype, the predicted phenotype (i.e. efficacy of various opioid or SSRI medications), other considerations, and treatment recommendations

#### **PGx Panel Testing**

For all trials, the PGx testing panel includes two required genes: *CYP2C19* and *CYP2D6*. The list of drugs with responses affected by these genes that will be the focus of recommendations in the trial are found in **Table 1**. Reflecting the pragmatic nature of the trial, there may be site to site variability in the testing of specific variants due to site-specific institutional approvals. The minimal required set of *CYP2C19* and *CYP2D6* variants are listed in Appendix B.

**Table 1. Genes to be tested and drugs with CPIC recommendations**

Genes	Drugs
CYP2C19	citalopram, escitalopram, sertraline
CYP2D6	codeine, oxycodone, tramadol, hydrocodone, fluvoxamine, paroxetine

*CYP2D6* phenotypes will be inferred based on the activity scoring system as shown in **Table 2 and Table 3**. The activity score value of each allele (**Table 2**) is added together to determine the total activity score for the diplotype. The activity scores are converted to phenotypes per **Table 3**. The IM phenotype will be defined as an activity score of >0 to 0.75, not >0.75 to 1.0. As there is debate about

how to define the IM phenotype, we will have an *a priori* analysis plan to determine whether participants in the usual care arm with an activity score of >0.75 to 1 (who we will define as NM) have worse pain control or depressive symptoms than NMs with an activity score > 1 to 2. If an allele is duplicated, and it is unknown which allele is duplicated, then the AS may be a ranged number, resulting in a ranged phenotype. If the ranged phenotype is NM-UM, the individual will be treated clinically as is if they were a UM.

**Table 2. CYP2D6 allele to activity score**

Alleles	Activity value+
*1, *2	1
*9, *14, *17, *29, *41	0.5
*10	0.25
*3, *4, *5, *6, *7, *8	0

+ Lab reported results may use older versions of CPIC guidelines for activity value definitions

**Table 3. CYP2D6 phenotype by Activity Score**

Inferred CYP2D6 phenotype	CYP2D6 activity score (AS)
UM	> 2.0
NM	>0.75 to 2.0
IM*	>0 to 0.75
PM	0

\*This phenotype definition differences from current CPIC guidelines and may be different from what appears in the lab reported phenotypes

CYP2C19 phenotypes will be inferred from the genotypes, as shown in **Table 4**.

**Table 4. CYP2C19 phenotype by genotype**

Inferred CYP2C19 phenotype	Example CYP2C19 genotypes
UM	*17/*17
RM	*1/*17
NM	*1/*1
IM	*1/*2, *1/*3, *2/*17, *3/*17
PM	*2/*2, *2/*3, *3/*3

The CYP2C19 metabolizer phenotype and the CYP2D6 metabolizer phenotypes and/or activity scores will be included in the PGx testing report generated by the laboratory, which is then returned to the provider and deposited in the EMR, where available.

## Clinical Decisions Support / Clinical Recommendations

### Acute and Chronic Pain

Standardized clinical consult notes with or without pharmacogenetics expert consultations will be generated based on the genotype-inferred phenotype, and in the case of drugs including *CYP2D6* guidance, will include consideration of drug interactions.

For *CYP2D6*, those taking concomitantly a strong *CYP2D6* inhibitor (as defined by FDA guidance on drug interactions[28]) will be considered to have been pheno-converted to a PM and recommendations will be consistent with that for a PM. Examples of strong inhibitors include, but are not limited to: bupropion, fluoxetine and paroxetine. Moderate inhibitors include, but are not limited to: duloxetine and mirabegron and reduce *CYP2D6* activity scores by 50%, and thus the inferred phenotype will be based on the genotype activity score x 0.5. Activity scores that align with a given phenotype, and which will ultimately will be based on genotype and drug interaction data, are shown in Tables 2 and 3. A full list of strong and moderate inhibitors can be found in Appendix C.

While we will not be including oxycodone as a drug on which we will make recommendations in IMs and PMs, based on UF data and other data in the literature that make the importance of *CYP2D6* for the pain response unclear, there are data that suggest that *CYP2D6* UMs can have significant toxicities (especially respiratory depression).[1, 29-31] Thus, oxycodone will be a drug for which we will make strong recommendations about avoiding use in UMs.

Using a standardized consult note/CDS or pharmacogenetics expert consultation, recommendations will be made to avoid tramadol, hydrocodone, or codeine in PMs, IMs, and UMs and to use an alternative opioid (e.g. morphine, hydromorphone) or non-opioid (e.g. NSAID), as noted in Table 5. Consideration of tramadol as the first line opioid will be recommended for NMs. While not part of the primary hypothesis, for safety reasons, avoidance of oxycodone will also be recommended in UMs.

Additionally, where possible, the CDS will include a provider alert for actionable phenotypes, triggered when a relevant opioid medication is ordered that indicates the participant's genetic results, the predicted phenotype, other considerations, and treatment recommendations.

**Table 5. CDS summary for acute and chronic pain treatments**

Treatment	CYP2D6 Phenotypes				
	Ultra-rapid	Normal to Ultra-Rapid	Normal*	Intermediate**	Poor
Tramadol	Avoid	Avoid	Preferred opioid	Avoid	Avoid
Codeine	Avoid	Avoid	Acceptable	Avoid	Avoid
Hydrocodone	Avoid	Avoid	Acceptable	Avoid	Avoid
Oxycodone	Avoid	Avoid	Acceptable	Acceptable	Acceptable

\*Defined as activity score >0.75 and ≤ 2.0

\*\*Defined as activity score >0 and ≤ 0.75

### Depression

Clinical decision support in the form of computerized alerts, standardized clinical consult notes, and/or pharmacist consultations will be generated to guide prescribers on dosing or selection of SSRIs or selection of alternate antidepressants based on predicted phenotype. Recommendations on drug choice and starting dose will be made in accordance with CPIC guidelines and/or FDA label information for paroxetine, fluvoxamine, citalopram, escitalopram, and sertraline, as outlined in Table 6. Drug-drug interactions leading to pheno-conversion will be incorporated into recommendations. For CYP2D6, concomitant use of a strong inhibitor (listed above) will result in a predicted phenotype of poor metabolizer, and the effect of concomitant moderate inhibitor (listed above) will be estimated by multiplying the CYP2D6 activity score by 0.5.

**Table 6. CDS summary for antidepressant medications**

	CYP2D6 Phenotypes				
	Ultra-rapid	Normal to Ultra-rapid	Normal	Intermediate	Poor
Paroxetine	Avoid	Avoid	Acceptable	Acceptable	Avoid or 50% Dose Reduction*
Fluvoxamine	No recommendation	No recommendation	Acceptable	Acceptable	Avoid or 25-50% Dose Reduction*
	CYP2C19 Phenotypes				
	Ultra-rapid and Rapid		Normal	Intermediate	Poor
Citalopram	Avoid		Acceptable	Acceptable	Avoid or 50% Reduction**
Escitalopram	Avoid		Acceptable	Acceptable	Avoid or 50% Reduction*
Sertraline	Monitor for Non-response		Acceptable	Acceptable	Avoid or 50% Reduction*

\* Dose reductions refer to starting dose of medication; Avoid refers to recommendation to switch to a drug not predominantly metabolized by the listed drug metabolizing enzyme. No recommendation refers to a scenario where CDS is not triggered but the drug is also not offered as an alternative given the phenotype.

\*\* Per the FDA warning, citalopram 20 mg/day is the maximum recommended dose in CYP2C19 poor metabolizers due to the risk of QT prolongation

## Context of the intervention implementations

Reflecting the pragmatic nature of the clinical trial, the intervention may be implemented in environments in which there are existing PGx testing and CDS. The PGx testing may be completed as part of larger, CLIA validated, PGx panel that include optional gene-drug pairs (Table 7). Additionally, clinical decision support may be in place for the study gene-drug pairs as well as other CPIC drug-gene pairs and/or other drugs affected by the study genes.

**Table 7. PGx panel genes and drugs with CPIC recommendations**

Genes	Drugs
CYP2C19 (Required)	amitriptyline, clopidogrel, clomipramine, doxepin, imipramine, trimipramine, voriconazole, omeprazole, esomeprazole, pantoprazole, lansoprazole, dexlansoprazole
CYP2D6 (Required)	amitriptyline, clomipramine, desipramine, doxepin, imipramine, nortriptyline, ondansetron, trimipramine, tropisetron
CYP2C9	warfarin, phenytoin
CYP3A5	Tacrolimus
SLCO1B1	Simvastatin
TPMT	azathioprine, mercaptopurine, thioguanine
NUDT15	azathioprine, mercaptopurine, thioguanine
VKORC1	Warfarin
CYP4F2	Warfarin

## 7.2 Baseline Participant Assessments

All study participants will complete baseline surveys for demographics and participant reported outcomes (PROs) (see Table 8 for details). These data will be collected by the study coordinator in person or alternatively by using telephone, email, or text.

Baseline data will be collected for the Chronic Pain and Depression trials following consent, for the Acute pain trial, survey data will be collected before surgery. The type of surgery information will be collected after the completed procedure.

*Participant demographics* – including but not limited to age, sex, gender, race, Hispanic/Latino ethnicity (Yes or no), and smoking status will be administered at baseline as a survey.

*Past medical history* – A snapshot of the participant's medical history. See MOP for details.

*Baseline medications* - Participant medications will be collected through the EHR and/or participant self-report. See MOP for details.

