## PROTOCOL VERSION AND AMENDMENT TRACKING

Version Number/ Affected Section(s)	Summary of Revisions Made	Approval Date
Randomization 4.1	Removed text: ... and revealed after baseline data are collected so study assignment does not impact the baseline survey responses.	9/15/2020
Safety Assessment and Monitoring 8	Deleted text...This is an observational study that does not include a drug or device intervention.	9/15/2020
Analysis of the Primary Endpoint 10.4	
Depression – text deleted ...Pediatric depression T- scores will be converted to adult depression T-scores using a published crosswalk linking the scores from the two surveys.
 
Added text: Pediatric depression T- scores will be transformed to the adult scale using a published crosswalk for a combined analysis.
	9/15/2020
Specimen Collection Section 7.4	Clarification that DNA specimen collection should be done after consenting and completed prior to randomization	12/22/2020
Throughout the Document	Removal of Quick Inventory of Depressive Symptomatology (QIDS) depression scale and replaced with Patient Health Questionnaire-8 (PHQ-8) depression scale.	7/2/2021
Protocol Synopsis-Inclusion Criteria Section 1	Acute Pain: • Removal of “Elective/planned surgery patients with an upcoming pre-surgery visit”	7/2/2021
Inclusion Criteria Section 5.1	
Chronic Pain:
 
 
• Removal of “as this is the minimum age at which proposed outcome measures (PROMIS) are validated without parent proxy” at age inclusion
 
• Added clarifying text for targeted opioids for Elective/planned surgery types
 
	

	
clinics definition and for treatment of chronic pain with specific opioids
 
 
Removed medical diagnosis codes for pain diagnosis, and symptoms
 
 
Depression:
 
 
Removal of “as this is the minimum age at which proposed outcome measures (PROMIS) are validated without parent proxy” at age inclusion
 
Added clarifying text for psychiatry and primary clinics definition and depression diagnosis
 
Removed medical diagnosis codes for depression
 
	

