#### **4.1 Randomization**

After participants provide informed consent/assent, participants will be randomized in a 1:1 allocation to the Intervention (i.e. immediate PGx testing and genotype-guided opioid or SSRI therapy with clinical decision support) and Control (i.e. usual care with delayed PGx testing) arms. Randomization will be stratified by trial and site or clinic with a random block size within each site or clinic. We anticipate variability in patient populations between recruiting sites or clinics and aim to balance the intervention assignments within the site or clinic unit. Additionally, the randomization for the chronic pain trial will be stratified by presence/absence of depression, and the randomization for the acute pain and depression trials will be stratified by pediatric/adult.

The randomization scheme will be generated by an unblinded statistician. Randomization assignments will be generated in real time in REDCap at the Coordinating Center.

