#### **4.2 Blinding**

ADOPT PGx randomization assignments will not be blinded to the participants or their providers but will be masked to the UF call center personnel who may be administering some of the participants follow-up surveys. Due to the nature of the intervention, it is impossible to completely mask participants and providers from the pharmacogenetic testing and return of results, hence participants, providers, and local study personnel will not be blinded. While the UF call center personnel administering follow-up surveys will be masked from the results and randomization, study-arm specific questions in the final (6 month) survey may reveal study arm randomization. Additionally, participants may volunteer to reveal their randomization or PGx testing results. If the randomization or phenotype is revealed to the call center, prior to administering the 6 month surveys, it will be documented in the database.

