## 7.4 Specimen Collection

DNA sample collection can be whole blood by venipuncture, saliva, buccal swab, or mouthwash, whichever is most appropriate for the site or study participant preference. The sample collection can occur in person or by mailed kits after consenting.

Once sample collection is completed, participants are randomized to a trial Control or Intervention arm. All DNA sample types and collection processes are detailed in the MOP.

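### Chronic pain and depression trials: the text lets a self-reported baseline be taken after the open-label arm is known, although both primary endpoints are change from baseline

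*Combined protocol and SAP*

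**What the plan says.** **Baseline timing.** Section 7.2: "Baseline data will be collected for the Chronic Pain and Depression trials following consent". This sets an earliest time but no latest time. The study coordinator collects the surveys in person or by telephone, email or text. The Baseline column of Table 8 has no window, although every follow-up column has one.

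**What triggers randomisation.** Section 4.1: "After participants provide informed consent/assent, participants will be randomized in a 1:1 allocation". Section 7.4 adds the DNA sample: "Once sample collection is completed, participants are randomized to a trial Control or Intervention arm". Neither mentions the surveys.

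**Blinding.** Section 4.2: "ADOPT PGx randomization assignments will not be blinded to the participants or their providers", "hence participants, providers, and local study personnel will not be blinded". The masked call centre is described for follow-up surveys only.

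**Endpoints.** Sections 3.1 and 10.4 define both primary endpoints as change from baseline to 3 months in a patient-reported score. Section 10.4 compares them with a two-sample t-test (or Mann-Whitney in chronic pain) without baseline adjustment. The synopsis analysis paragraph words the depression comparison as 3-month scores, but its own endpoint definition and sections 3.1 and 10.4 say change.

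**History.** The amendment log records that on 9/15/2020 the words "and revealed after baseline data are collected so study assignment does not impact the baseline survey responses" were removed from section 4.1. This helps explain why the current text has no such rule. A difference between the log and the current text is not itself an error, and the point does not rest on it.

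**The concern.** A participant who already knows whether testing is immediate or delayed by six months may rate current pain or low mood differently because of that knowledge. The coordinator taking the answers may know the arm as well. If the answers shift by arm, randomisation no longer protects the baseline, and the shift passes straight into the change score. The planned comparison cannot separate it from a treatment effect.

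There are two secondary consequences. Section 10.6 plans covariate-adjusted models because baseline differences may arise within the phenotype subgroups; without a rule on order, such differences cannot be told apart from arm-aware reporting. Section 10.8 uses baseline pain or depression scores to examine the missing-at-random assumption, so that check would be affected too.

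**Working it through.** **1. Order of steps.**

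| Step | Must follow | Must precede |
|---|---|---|
| DNA sample (7.4) | consent | randomisation |
| Randomisation (4.1, 7.4) | consent and DNA sample | nothing tied to the surveys |
| Baseline surveys, chronic pain and depression (7.2) | consent | not stated |

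Consent, sample, randomisation, arm known, baseline survey is therefore a permitted order. It is also a realistic one: kits may be mailed (7.4) and surveys may be remote (7.2), so these can be separate tasks, and only the sample triggers randomisation.

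**2. The plan's own sample sizes reproduce.** Exact two-sample t-test, two-sided alpha 0.049, 90% power (section 10.1):
- Chronic pain, effect 0.40: 133.02 per arm, rounded up to 134 (stated 134). Power at 134 is 90.2%.
- Depression, effect 0.28: 270.45 per arm, rounded up to 271 (stated 271). Power at 271 is 90.1%.

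**3. How a shift enters the endpoint.** Let change = 3-month score − baseline. Suppose a share *p* of baselines is taken after the arm is known, the arms' answers then differ by *s*, and the true effect is zero.
- Unadjusted difference in change = 0 − *p·s*, so the bias has size *p·s*.
- Adjusting for baseline with slope β gives 0 − β·*p·s*. The bias is rescaled, not removed, because the covariate itself depends on the arm.

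**4. Assumed range.** The documents give no values. Taking *p* = 20-50% and *s* = 0.1-0.3 SD:
- low: 0.2 × 0.1 = 0.02 SD
- high: 0.5 × 0.3 = 0.15 SD

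These are treated as SDs of the change score. If *s* is in SDs of the baseline score, multiply by SD(baseline)/SD(change), a ratio the documents do not give.

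**5. False-positive rate when the shift imitates an effect.** Noncentrality λ = b·√(n/2), with √(134/2) = 8.185 and √(271/2) = 11.640. Critical |t| is 1.978 on 266 df and 1.973 on 540 df.

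| Shift b | Chronic pain λ | False positive | Depression λ | False positive |
|---|---|---|---|---|
| 0 | 0 | 4.9% | 0 | 4.9% |
| 0.02 | 0.164 | 5.2% | 0.233 | 5.5% |
| 0.10 | 0.819 | 12.7% | 1.164 | 21.1% |
| 0.15 | 1.228 | 22.9% | 1.746 | 41.1% |

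**6. Power when the shift works against the intervention.** Same test with effect d − b:

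| Shift b | Chronic pain d − b | Power | Depression d − b | Power |
|---|---|---|---|---|
| 0.02 | 0.38 | 87.1% | 0.26 | 85.4% |
| 0.10 | 0.30 | 68.4% | 0.18 | 54.9% |
| 0.15 | 0.25 | 52.8% | 0.13 | 32.4% |

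Depression is the more exposed because its planned effect is smaller and its sample larger.

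**The case against.** **The order may be fixed elsewhere.** Section 7 calls itself an overview, sites are trained on the MOP, and allocation runs in REDCap, where an order could already be enforced. The MOP, the REDCap build and the separate SAPs were not available. This stands as a limit. However, section 7.2 cites the MOP for medical history and medications, not for the timing of surveys.

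**The intent is probably baseline first.** Section 7.3 speaks of post-intervention collection and counts control-arm follow-up from the baseline assessments. Results take about one week from sampling on average, so before then participants would know only whether testing is immediate or delayed, not their phenotype. This makes large shifts less likely. It is not a rule about randomisation.

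**Some information is needed before randomisation.** Section 4.1 says "the randomization for the chronic pain trial will be stratified by presence/absence of depression". The source of that factor is not stated to be the baseline survey. It would not secure the pain-intensity baseline, and it does not apply to the depression trial.

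**Stronger readings that the documents do not support.** A reader might infer that baselines were in fact taken late, or that the deletion in the log proves it; the text shows only what is permitted. A reader might also extend the point to the acute pain primary endpoint, since "for the Acute pain trial, survey data will be collected before surgery" and results could be back by then. That endpoint is the 10-day SIA score with no baseline term (10.4), so this mechanism does not bias it. Finally, the 12.7% and 21.1% at a shift of 0.10 SD are one point on an assumed range, not estimates.

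**Conclusion.** The gap is real in the chronic pain and depression trials and should be closed. The stated triggers for randomisation allow an avoidable, arm-dependent baseline to enter an open-label change-score endpoint, and no current section supplies the missing order.

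Its size and direction are unknown. Under the assumed shift of 0.02-0.15 SD the effect runs from negligible to large in both tables above. The calculation assumes that the shift is in SDs of the change score, that 3-month answers are unaffected, that the planned analysis numbers are reached, and that the t-test is used. If the MOP already requires baseline surveys first, what remains is a one-sentence documentation point.

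**What to change.** **Text.** State in sections 4.1, 7.2 and 7.4 that baseline patient-reported surveys are completed before the assignment is generated, or at least before it is revealed. If the MOP already says so, cite it there.

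**System.** For any remaining enrolment, make survey completion a required field before REDCap releases the allocation, and record both time stamps. Enrolment status is not stated, so this may help only part of the sample.

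**Participants already enrolled.** Report by arm the number and timing of baselines dated after randomisation. Add a sensitivity analysis of the primary endpoint, for example:
- comparing 3-month scores without using the late baseline, which excludes no one for a late survey; or
- excluding participants with late baselines. This conditions on a post-randomisation event that may differ by arm, so it is supportive only.

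**Cost.** A sentence in three sections, one REDCap gate and one supplementary table and analysis. Some randomisations would be delayed while a survey is completed.
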